The unblinded nature of the participants and researchers is offset by the outcomes measured from the CGM glucose reports of the study participants.

There is a potential for participants to learn that the lower threshold may be beneficial and continue to use the revised threshold. However, all participants will be informed about the nature of the study design and encouraged to adhere to the specified thresholds of the study.

Blinding and Randomisation

This is an open-label study; study is not blinded

Device Tracking

Not applicable

Intervention/Product Description

Not applicable

Product Accountability Procedures

Not applicable

Trial Duration/Schedule

Each participant will be in the study for 10 weeks. Expected study duration to completion of visits is 18 months.

Trial Termination

Study participation is voluntary, and participants may withdraw at any time.

In general, once a participant is in the study, he/she will remain in the study unless the investigator believes it is not safe for the participant to continue. The criteria below will be used to determine safety:

1. *Severe hypoglycaemia* (seizure or coma or any episodes of hypoglycaemia with altered consciousness requiring glucagon).
2. *Non-adherence* to the protocol or development of a new medical condition or need for chronic use of a medication which in the judgment of the investigator increases risk for the participant.

Criteria for Suspending/Stopping Overall Study:

Criteria will be developed in conjunction with DSMB members at the first meeting.

The primary safety outcome will be severe hypoglycaemia defined objectively as coma/convulsion. The background rate of severe hypoglycaemia is low 3 per 100 patient years (2015) ²⁰ and 2 per 100 patient years in the 2023 quarterly clinical review.

As severe hypoglycaemia events are experienced during the study, the DSMB will be notified in real-time. The DSMB will review if the event was caused due to the intervention.

At any time in the study, if two participants in the intervention arm have experienced severe hypoglycaemia resulting in coma or convulsion due to the intervention, the trial will be suspended. The DSMB will be called for an emergency review to discuss the early termination of the trial due to safety concerns.

The DSMB will notify the Principal Investigator and the Trial Management Group (TMG) if the study should be stopped. This will be conveyed to the ethics committee within 72h of the DSMB notification.

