Data identification

The identification of any data to be recorded directly on the Case Report Forms (CRFs) (i.e. no prior written or electronic record of data), and to be considered to be source data.

5 Source and Selection of Participants

Source of Participants

This study aims to recruit children living with T1D and attending the Diabetes Clinic at PCH. Currently, there are approximately 1200 children and adolescents with diabetes, residing in Western Australia with 60% on insulin pump therapy and an increasing number of children on AHCL (n~400) as standard care.

Patients with T1D who satisfy the inclusion criteria, and consented to be contacted for research purposes, will be identified from the existing clinic database (Western Australian Children's Diabetes Database, WACDD) (HREC 2012051EP) by a Child and Adolescent Health Service employee and invited via email to partake in this study. Information on the study will also be disseminated via clinic newsletter and social media.

Participant inclusion criteria.

1. Diagnosis of Type 1 diabetes
2. 6 to 18 years
3. Duration of diabetes of >12 months (to ensure families have gained experience in managing hypoglycaemia)
4. On advanced closed loop therapy
 - 4.1 for at least 4 weeks and
 - 4.2 using the system optimally for >80% in last 2 weeks.

Participant exclusion criteria.

1. Impaired hypoglycaemia awareness. Self-reported Gold score ≥ 4 (these patients need higher glucose targets). For young children (age 6 to 10 years or if the child is developmentally young to self-report, parent-reported response will be used).
2. Increased time spent in hypoglycaemia as documented on CGM (>2% of time spent < 3.0 mmol/L and/or >6% of time spent < 3.9 mmol/L) for last two weeks
3. Families not willing to try lower cut-off due to fear of hypoglycaemia.
4. Severe hypoglycaemia (coma, convulsion or altered consciousness requiring third party assistance) in last 12 months.
5. Any medical or psychological disease state of the child and/or caregiver that limits capacity to participate in the study.

Participant withdrawal criteria

(a) when and how to withdraw participants from the investigational product/trial treatment; Participants will be informed that they can withdraw from the study at any time. They can do so by contacting the research team.

(b) the type and timing of the data to be collected for withdrawn participant(s); All data for withdrawn participant will be used for analysis.

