2. Although the revised hypo treatment is to initiate treatment ≤ 3.6 mmol/L, treatment of glucose level < 3.9 mmol/L is recommended if there are downward trend arrows on sensor, active insulin on board and precedent activity/exercise. All families are educated on decision making with CGM trend arrows around hyperglycaemia/hypoglycaemia management.

The benefits to the participants are that they may achieve better glycaemic control with a reduction in overtreatment with hypoglycaemia.

Safety

- a. The sensor glucose levels of all study participants are available to participants in real-time which will enable them to take appropriate clinical action as required.
- b. Urgent low notification at < 3.0 mmol/L or 3.1 mmol/L is default (factory-set) and will be 'on' for all participants at all times. Carers will also have this feature on their phone as part of remote monitoring.
- c. Low notification will be set at 3.6mmol/L during the 'Revised Hypo Rx' phase and at <3.9 mmol/L for 'Standard Hypo Rx' phase.
- d. AHCL is dependent on the sensor glucose levels and basal insulin delivery will be adjusted based on sensor glucose readings. It is therefore expected to mitigate any significant risk of hypoglycaemia < 3.0 mmol/L.
- e. All participants are educated on the use of IM glucagon with severe hypoglycaemia (coma, convulsion, altered sensorium). This will be reviewed at Visit 1 as part of hypoglycaemia education.
- f. Establishment of a Data and Safety Monitoring Board
- g. All serious adverse events are to be recorded and reported to the investigators within 24hours.

Data and Safety Monitoring Board

A data and safety monitoring board (DSMB), consisting of an endocrinologist, a statistician and a clinical trial specialist, will be established to safeguard the interests of the trial participants and monitor the overall conduct of the study. The board will receive and review information on the progress and accruing data and provide advice on the conduct of the trial to the Principal Investigator and the Trial Management Group (TMG)*. The Principal Investigator and the TMG are required, under the DSMB charter for the study, to follow the DSMB's directions regarding the safety of the trial.

*The Trial Management Group, consisting of the research endocrinologist, the research nurse and the project manager, will be in charge of the day-to-day activities of the study.

Adverse event reporting

Adverse Event

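### The automatic suspension rule counts coma or convulsion only if judged caused by the intervention, a condition that prevents at most about 0.4% of needless pauses and can only make the rule fire less often

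*Protocol*

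**What the plan says.** Section 4, Trial Termination, opens the trial-level criteria by deferring them: "Criteria will be developed in conjunction with DSMB members at the first meeting". It then defines the primary safety outcome as coma or convulsion and gives background rates of 3 (2015) and 2 (2023) per 100 patient-years. On handling of events it says "As severe hypoglycaemia events are experienced during the study, the DSMB will be notified in real-time" and "The DSMB will review if the event was caused due to the intervention". One rule is fixed at once: "if two participants in the intervention arm have experienced severe hypoglycaemia resulting in coma or convulsion due to the intervention, the trial will be suspended". An emergency DSMB review of early termination follows that suspension.

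Three other places bear on the point:

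- The participant-level safety criteria in the same section list severe hypoglycaemia ("seizure or coma or any episodes of hypoglycaemia with altered consciousness requiring glucagon") without asking about cause.
- Section 5 excludes children with "Severe hypoglycaemia (coma, convulsion or altered consciousness requiring third party assistance) in last 12 months", and those with a Gold score of 4 or more.
- Section 8 (Data and Safety Monitoring Board) obliges the investigator and the Trial Management Group "to follow the DSMB's directions regarding the safety of the trial".

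**The concern.** An attribution condition in a stopping rule protects against pausing a trial for events that would have happened anyway. It is worth having when background events are common. Here they are rare and exposure is short, so two affected children would already be a strong signal without a ruling on each one.

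Attribution is also difficult for this intervention. It is a treatment threshold, and children in the revised phase must still treat for symptoms, for downward trend arrows, for active insulin and around exercise. A single convulsion could often be put down to a bolus, to activity or to a sensor fault. The protocol prints no criteria for deciding. An outcome that the protocol calls objective thus acquires a subjective filter at the one point where the response was meant to be automatic.

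What is at stake is a delayed pause in a paediatric trial that deliberately postpones treatment of low glucose.

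**Working it through.** **Inputs**

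- Participants: 40 recruited, 36 after 10% drop-out (Section 9, Sample Size). In a cross-over design each is due to spend time on the revised threshold.
- Exposure: 4 weeks (28 days) per participant on the revised threshold (Section 4, Study Design; Section 6 table).
- Background rate: 2 to 3 per 100 patient-years (Section 4, Trial Termination), taken here as the rate of coma or convulsion.
- Trigger: at least 2 affected participants.

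**The plan's own figure.** The protocol gives no operating characteristic for the trigger. The sample size that fixes the exposure does reproduce. The margin over its standard error is 0.56/(0.96/√36) = 3.5, and power = Φ(3.5 − 1.96) = 93.8%, in line with the stated figure of over 90%. For drop-out, 36/0.9 = 40.

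**Exposure and expected events**

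- 40 × 28/365.25 = 3.07 patient-years (2.76 with 36).
- Expected background events: 3.07 × 0.02 = 0.061, and 3.07 × 0.03 = 0.092.

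**Chance of two affected participants with no harm**

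Per-participant risk: p = 1 − exp(−rate × 28/365.25), which is 0.00153 at 2 per 100 and 0.00230 at 3 per 100. Trigger probability: P(Binomial(n, p) ≥ 2) = 1 − (1−p)ⁿ − n·p·(1−p)ⁿ⁻¹.

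- n = 40, 2 per 100: 1 − 0.9405 − 0.0577 = 0.0018
- n = 40, 3 per 100: 1 − 0.9121 − 0.0840 = 0.0039
- n = 36: 0.0014 and 0.0032

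The most the causal condition can save is therefore about 0.2 to 0.4 percentage points. The background rate is a clinic figure, and the exclusions in Section 5 probably make the enrolled children's rate lower still.

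**What the condition can cost**

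The protocol gives neither a rate under harm nor an attribution probability, so both are assumptions. With rate multiplier f and attribution share a, p = 1 − exp(−rate × 28/365.25 × f × a). For f = 10 and n = 40:

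| Share attributed | 2 per 100 | 3 per 100 | Points lost |
|---|---|---|---|
| No condition | 12.4% | 23.1% | – |
| 90% | 10.4% | 19.8% | 2.0–3.3 |
| 75% | 7.7% | 14.9% | 4.7–8.1 |
| 50% | 3.8% | 7.7% | 8.6–15.4 |

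At a tenfold rate, 9 of every 10 events are truly caused, so the 90% row is a DSMB that attributes correctly. With correct attribution at smaller harms (only the excess rate, f − 1, is counted), the loss is 0.5–1.1 points at twofold, 0.8–1.6 at threefold and 1.3–2.5 at fivefold. In each case this exceeds the 0.18–0.39 points the condition can save at the same background rate.

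**How sensitive the rule is without the condition.** Setting the trigger probability to 50% at a = 1 gives f = 27.7 from 2 per 100 and f = 18.5 from 3 per 100.

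**The case against.** The strongest reply is that the protocol already covers this risk. The DSMB hears of every severe event in real time, so the first event reaches an independent board without waiting for a second. Its safety directions are binding, and further criteria are to be set at its first meeting. Weekly review with escalation and 24-hour reporting of serious events add to this. Requiring relatedness before suspending a whole trial is a defensible choice, and deleting the requirement still leaves an insensitive rule.

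Much of that stands. The DSMB can pause the trial earlier, and the two-participant count is the larger limit. The tenfold rate has no source in the protocol, and the 50% row supposes a board that misses nearly half of the caused events. With correct attribution, each pause lost is a trial in which fewer than two children had a caused event, so calling all of these missed true pauses would overstate the point. The contrast with the participant-level criteria is also softer than it looks, because those depend on the investigator's judgement and serve a different purpose.

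None of this changes the rule as written. The board's other powers are discretionary, whereas an automatic trigger exists so that a pause does not rest on discretion. Criteria still to be developed may supplement this one, but it is already fixed.

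The 0.4% figure does depend on counting only the four weeks on the revised threshold. Counting all 10 study weeks gives 1.0% to 2.2%, but that would treat standard-care and wash-out weeks as time in the intervention arm, which is not the natural reading.

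**Conclusion.** The concern holds as a modest, low-cost safety improvement. The causal condition removes at most about 0.4 percentage points of needless pauses (0.18% to 0.39% with 40 participants), and by construction it can only reduce the chance of suspension. That much rests on the protocol's own background rate, independent participants each counted once, a constant rate, and events counted only during the revised-threshold weeks.

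How many warranted pauses it would block cannot be computed from the document, because that depends on how the DSMB attributes events; the tenfold figures are illustrations. The trial's efficacy conclusions are not affected.

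**What to change.** In Section 4, Criteria for Suspending/Stopping Overall Study, delete the four-word causal qualifier at the end of the trigger condition. Any two participants with coma or convulsion while on the revised threshold would then lead to suspension and emergency DSMB review. State that causality is judged in that review and decides whether the trial restarts or stops. Naming time on the revised threshold, rather than an arm, would also make the counting window clear in a cross-over.

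The cost is one phrase and at most about a 0.4% chance of an unnecessary temporary pause. The edit does not cure the insensitivity that comes from requiring two participants.

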Real-world data from children on AHCL at our centre was recently evaluated. The median (IQR) time spent in hypoglycaemia <3.0 mmol/L was 0.2 (0.1-0.5)²¹. The distribution was approximately log normal with a mean (SD) of -1.3 (1.2). To inform the power calculation of this study, the paired difference in the log transformation of time < 3.0 mmol/L (%) in participants on closed loop therapy over the period of 12 weeks was reviewed. The distribution of the paired difference in the log-transformed '% time <3.0 mmol/L' was roughly normal with a standard deviation of 0.96.

A non-inferiority limit was identified based on discussions with clinicians and was set at a 75% increase in time spent in hypoglycaemia. This equates to a difference of 0.56 in the log-transformed time <3.0 mmol/L.

A sample of 36 participants would provide over 90% power for the boundary of a one-sided 97.5% confidence interval (one sided alpha of 0.025) to fall below the non-inferiority limit of 0.56. Allowing for 10% drop-out, we will recruit 40 participants.

Study Power and Significance

The primary analysis will have 90% power and a one-sided alpha of 0.025. For all secondary outcomes, alpha will be set at 0.05.

Statistical plan deviations

Any deviations to the original statistical plan will be reported to relevant ethics committees as an amendment to the scientific protocol and in the manuscript.

Selection of participants for analyses

All participants enrolled in the study will be included in the analysis.

Data management

Any information collected in connection with this project will remain confidential. Following consent, the participant will be provided with a unique study number which will be used on data collection instruments in place of identifying information to protect participant confidentiality.

All paper records will be stored in locked cabinets in the Endocrinology/diabetes office space on Level 2 at PCH. Electronic data will be stored on password protected CAHS REDCap database and the W:\Endocrinology\PMH\Endo Research\Departmental\study folder, which are accessible only by the study team.

On completion of the project, data analysis and publication of the project outcomes, the paper records will be archived as per PCH archiving policy. All records will be retained for 25y after publication of the study findings, after which they will be destroyed as per CAHS policies for research data management.

Procedures for missing, unused and spurious data:

Multiple imputation will be used to account for missing data in regression models.

10 Monitoring / Audit

Monitoring, Audit and Regulatory Inspections Statement

The trial investigators will permit trial-related monitoring, audits, and regulatory inspections, providing direct access to source data/documents

Procedures for monitoring and auditing

The study is monitored by the coordinating principal investigator monthly.

11 Quality Control and Quality Assurance

Compliance statement

The trial will be conducted in compliance with the protocol, Good Clinical Practice and the application regulatory requirements.

Quality control

All staff will be trained to ensure appropriate data collection in accordance with ICH-GCP guidelines. They will be trained on how to fill out the CRFs to ensure quality of data. Research nurse is an experienced diabetes educator with vast experience in clinical research trials.

12 Ethics

Participants are informed that their consent is voluntary and their participation in the trial or not will not affect their treatment in the clinic.

13 Budget, Financing, Indemnity and Insurance

This is an investigator-led project. All investigators and study personnel are indemnified by CAHS. Project cost covered by PCH Foundation.

14 Publication

The study will be registered at Australia New Zealand Clinical Trial Register (ANZCTR). Final results will be disseminated in a publication and presented at local and international conferences. All participants will be informed about the findings via newsletter and emails.

15 References

1.1 Parent version (for child < 12 years)

1.1.1 Behaviour scale

This survey is intended to find out more about how low blood sugar makes people feel and behave. Please answer the following questions as frankly as possible about how you felt during the past month.

Below is a list of things **parents** of children with diabetes sometimes DO IN ORDER TO AVOID LOW BLOOD SUGAR and related problems in their children. Read each item carefully. Circle one of the numbers that best describes **YOU** during the past month.

	0=NEVER	1=RARELY	2=SOMETIMES	3=OFTEN	4=ALMOST ALWAYS
1 Have my child eat large snacks at bedtime	0	1	2	3	4
2 Avoid having my child being alone when his/her sugar is likely to be low	0	1	2	3	4
3 Allow my child's blood sugar to be a little high to be on the safe side	0	1	2	3	4
4 Keep my child's sugar higher when he/she will be alone for awhile	0	1	2	3	4
5 Have my child eat something as soon as he/she feels the first sign of low blood sugar	0	1	2	3	4
6 Reduce my child's insulin when I think his/her sugar is too low	0	1	2	3	4
7 Keep my child's blood sugar higher when he/she plans to be away from me for awhile	0	1	2	3	4
8 Have my child carry fast-acting sugar	0	1	2	3	4
9 Have my child avoid a lot of exercise when I think his/her sugar is low	0	1	2	3	4
10 Check my child's sugar often when he/she plans to go on an outing	0	1	2	3	4
11 Get up in the middle of the night to check on my child or check my child's blood sugar levels	0	1	2	3	4

1.1.2 Worry scale

Worry: Below is a list of **concerns** parents of children with diabetes sometimes have.

Read each item carefully.

Circle one of the numbers that best describes
HOW OFTEN YOU WORRY ABOUT EACH ITEM

	0=NEVER	1=RARELY	2=SOMETIMES	3=OFTEN	4=ALMOST ALWAYS			
12				0	1	2	3	4
13				0	1	2	3	4
14				0	1	2	3	4
15				0	1	2	3	4
16				0	1	2	3	4
17				0	1	2	3	4
18				0	1	2	3	4
19				0	1	2	3	4
20				0	1	2	3	4
21				0	1	2	3	4
22				0	1	2	3	4
23				0	1	2	3	4
24				0	1	2	3	4
25				0	1	2	3	4
26				0	1	2	3	4
27				0	1	2	3	4
28				0	1	2	3	4

1.2 Child version (for children > 12 years)

1.2.1 Behaviour scale

We want to find out more about what low blood sugar makes young people feel and do.
Please answer the questions below as honestly as you can.

Below is a list of things young people with diabetes sometimes DO TO KEEP FROM HAVING LOW BLOOD SUGAR. Circle the number that best describes YOU.

	0=NEVER	1=RARELY	2=SOMETIMES	3=OFTEN	4=ALMOST ALWAYS
1 Eat large snacks at bedtime	0	1	2	3	4
2 Try not to be by myself when my sugar is likely to be low	0	1	2	3	4
3 Keep blood sugars a little high to be on the safe side	0	1	2	3	4
4 Keep blood sugar higher when I will be alone for a while	0	1	2	3	4
5 Eat something as soon as I feel the first sign of low blood sugar	0	1	2	3	4
6 Take less insulin when I think my blood sugar might get too low	0	1	2	3	4
7 Keep my blood sugar higher when I am going to be away from home	0	1	2	3	4
8 Carry some kind of sugar, drink, or food with me	0	1	2	3	4
9 Try not to do a lot of exercise when I think my sugar is low	0	1	2	3	4
10 Check my blood sugar often when I go away from home	0	1	2	3	4

[figure not shown]
1.2.2 Worry scale

Below is a list of things that young people with diabetes sometimes worry about concerning low blood sugars.

Circle the number that best describes YOU

	0=NEVER	1=RARELY	2=SOMETIMES	3=OFTEN	4=ALMOST ALWAYS
11 Not recognizing that my blood sugar is low	0	1	2	3	4
12 Not having food, fruit, or juice with me when my blood sugar gets low	0	1	2	3	4
13 Feeling dizzy or passing out in public because of low blood sugar	0	1	2	3	4
14 Having a reaction while asleep	0	1	2	3	4
15 Embarrassing myself because of low blood sugar	0	1	2	3	4
16 Having a reaction while I am by myself	0	1	2	3	4
17 Looking "stupid" or clumsy in front of other people	0	1	2	3	4
18 Losing control because of low blood sugar	0	1	2	3	4
19 No one being around to help me during a reaction	0	1	2	3	4
20 Making a mistake or having an accident at school	0	1	2	3	4
21 Getting in trouble at school because of something that happen when my sugar is low	0	1	2	3	4
22 Having seizures	0	1	2	3	4
23 Getting long term complications from low blood sugar	0	1	2	3	4
24 Feeling dizzy or woozy when my blood sugar is low	0	1	2	3	4
25 Having a low blood sugar	0	1	2	3	4

2. ISPAD Hypoglycaemia Management (2022 Guidelines)

3. Questionnaire on Glucose Threshold for Hypoglycaemia

Thank you for participating in the study.

1. Do you believe there is a need to change the current treatment recommendation to treat glucose level < 3.9 mmol/L? If yes, why? If no, why?

2. Do you think we should have one glucose level for hypo treatment for all or should we have this level personalised to the child/family?

3. On a scale of 1-5 where 1 = very easy and 5 = very hard:

Very easy	Easy	Neutral	Hard	Very hard
1 	2 	3 	4 	5 

How comfortable were you with treating hypo at a glucose level \leq 3.6mmol/L mmol/L?

If you scored 3/4/5 (neutral/hard/very hard), can you elaborate?

4. While treating hypo at a glucose level \leq 3.6mmol/L, did you feel that you/your child spent more time below 3 mmol/L?

5. Were there any other situations, other than downward CGM arrows, post meal insulin bolus or exercise that you would do a hypo treatment for glucose < 3.9 mmol/L.

6. Any other comments?

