The study aims at determining if reducing the glucose level of initiating treatment will be an acceptable hypoglycaemia threshold and will not be associated with an increase in time spent in hypoglycaemia <3.0 mmol/L with worsening of glycaemic outcomes in children and adolescents with T1D on AHCL.

Hence, the primary aim of the study is

To determine whether hypoglycaemia treatment initiated at a lower glucose threshold is non-inferior to the standard glucose threshold of <3.9 mmol/L with regards to *time spent in clinically significant hypoglycaemia* (sensor glucose <3.0 mmol/L) in children and adolescents on AHCL.

Secondary aims are

1. To explore the impact of standard vs revised hypoglycaemia treatment on *glycaemic outcomes*: time spent in target glucose range of $3.9-10$ mmol/L and time spent in hyperglycaemia > 10 mmol/L, > 13.9 mmol/L.
2. To determine whether hypoglycaemia treatment initiated at a lower glucose threshold is acceptable for the child with T1D and their families.

HYPOTHESIS

Time spent in clinically significant hypoglycaemia (< 3.0 mmol/L) will not be worse with revised hypoglycaemia threshold on closed loop therapy.

4 Trial Design

The scientific integrity of the trial and the credibility of the trial data depend substantially on the trial design and methodology.

Study Endpoints

[figure not shown]
Primary outcome: Time spent in hypoglycaemia <3.0 mmol/L (Recommended to be $<1\%$)¹

Secondary outcomes:

1. CGM-derived Glycaemic metrics: Time in range $3.9-10$ mmol/L (Recommended to be $>70\%$), Time spent in hyperglycaemia >10 and >13.9 mmol/L (Recommended to be $<25\%$ and $<5\%$ respectively)¹
2. Open-ended questions to determine participant's acceptability of revised hypoglycaemia cut-off.

Study Design

This will be a single-centre cross-over randomised controlled study. A two-treatment, two-period cross-over randomised controlled non-inferiority trial design will be used. Participants will be randomised to sequence A ('Standard Hypo Rx First'), or sequence B ('Revised Hypo Rx First'). Figure shows the study design.

'Standard Hypo Rx First' participants will use the standard hypo treatment⁵ (i.e. Hypoglycaemia treatment initiated with glucose level <3.9 mmol/L) for 4 weeks (Period 1) after which they will switch to revised hypo treatment plan for 4 weeks (Hypoglycaemia treatment initiated at lower revised threshold of 3.6 mmol/L) (Period 2).

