Visit 2:

End of Period 1 (F2F / telehealth) (30min)

Participants will finish Period 1 and commence wash-out period for 2 weeks. In the wash-out period, hypo treatment will be treatment as usual (standard hypo treatment).

1. Diabetes clinical
 - a. CGM metrics: Time spent in hypoglycaemia, Time in range, Time in hyperglycaemia and glycaemic variability
 - b. Total daily dose of insulin (mean of previous 7 days)
2. Psychology measures:
 - a. Fear of hypoglycaemia: Hypoglycaemia fear survey Child and Parent¹⁹
3. Any adverse events/severe adverse events

Visit 3:

Start of Period 2 (F2F / telehealth) (1 hour)

Standard Hypo Rx First' participants will switch to revised hypo treatment plan for 4 weeks.

'Revised Hypo Rx First' participants will switch to standard hypo Rx plan for 4 weeks.

All participants will receive weekly review with email/phone calls by our team. If time spent <3.0 mmol/L has doubled from baseline and/or is >1%, research staff (doctor and research diabetes educator) will review the participant to ensure 1) if they are 'true' hypoglycaemic events 2) explore the reason if 'true' hypoglycaemia.

Visit 4: End of Period 2/End of study (F2F / telehealth) (30 mins)

1. Diabetes clinical
 - a. CGM metrics: Time spent in hypoglycaemia, Time in range, Time in hyperglycaemia and glycaemic variability
 - b. History of severe hypoglycaemia – coma or convulsion or episodes requiring third party assistance (events in last 12 months).
 - c. History of diabetic ketoacidosis (DKA) in the last 12 months
 - d. Hospital admissions in the last 12 months (DKA, Hyperglycaemia, Hypoglycaemia, Non-diabetes related)
 - e. Total daily dose of insulin (mean of previous 7 days)
 - f. Co-morbidities and medications
2. Psychology measures:
 - a. Fear of hypoglycaemia: Hypoglycaemia fear survey Child and Parent¹⁹
3. Any adverse events/severe adverse events
4. Open-ended questions to understand acceptability

Bias

To minimise selection bias, the population of all children eligible for the study will be identified from the Diabetes Database and invited by email and follow up telephone call.

Multiple avenues of recruitment will be utilised to try to reduce the influence of self-selection bias. For example, participants who meet the inclusion criteria will be emailed an invitation or could be approached in the diabetes outpatient clinics and informed about the study during their clinic visit. Recruitment via social media will also be utilised.

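### Item 3 of the acceptability questionnaire asks about comfort but offers answers on an easy-to-hard scale, and only scores of 3 to 5 are asked to explain.

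*Protocol*

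**What the plan says.** Protocol section 3 gives the second secondary aim as "To determine whether hypoglycaemia treatment initiated at a lower glucose threshold is acceptable for the child with T1D and their families". Section 4, Study Endpoints, names the matching outcome as "Open-ended questions to determine participant's acceptability of revised hypoglycaemia cut-off", and the Visit 4 schedule lists "Open-ended questions to understand acceptability".

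The instrument is the third appendix in section 16, the Questionnaire on Glucose Threshold for Hypoglycaemia. It has six items, and only item 3 has a rating scale:

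- instruction: "On a scale of 1-5 where 1 = very easy and 5 = very hard", followed by five boxes that each carry a number and a verbal label from very easy to very hard;
- stem: "How comfortable were you with treating hypo at a glucose level" of 3.6 mmol/L or below;
- follow-up: "If you scored 3/4/5 (neutral/hard/very hard), can you elaborate".

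Item 1 asks whether the current treatment recommendation should change, with "If yes, why? If no, why". Item 4 asks whether the family felt that more time was spent below 3 mmol/L. Item 6 is "Any other comments". The protocol gives no scoring rule, cut-off or definition of acceptance for item 3.

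**The concern.** The question and the answers are about different things. The stem asks how the family felt; the boxes record how difficult the task was. A respondent has to decide which of the two to report, and the analyst cannot tell from the score which was chosen. The numbering adds a smaller problem: on a question about comfort, a higher number is naturally read as more comfortable, whereas here it means harder.

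The follow-up could resolve the ambiguity, but it is offered only at scores of 3 to 5. At scores of 1 or 2 nothing within the item shows what the respondent meant.

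At stake is the meaning of the one number that the trial will hold on acceptability. Item 3 is also the only question that asks families directly how they found treating at the revised level.

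**Working it through.** No figure in the protocol depends on this item, so there is nothing to recompute. The check sets the stem, anchors and follow-up rule side by side.

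**Step 1: what each part of item 3 refers to.**

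| Part | Refers to | A higher number means |
|---|---|---|
| Stem | comfort | more comfortable, on a natural reading |
| Instruction and box labels | ease or difficulty | harder |
| Follow-up | ease or difficulty (repeats the labels) | harder, and asked to explain |

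The instruction, labels and follow-up agree with one another. The stem is the part that does not fit.

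**Step 2: what happens to each kind of respondent.**

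| Experience | Answers by | Likely score | Asked to elaborate in item 3? |
|---|---|---|---|
| Easy and comfortable | labels | 1–2 | No |
| Hard and uncomfortable | labels | 4–5 | Yes |
| Easy but uncomfortable | labels | 1–2 | No |
| Hard but comfortable | labels | 4–5 | Yes |
| Uncomfortable | number only, reading high as comfortable | 1–2 | No |
| Comfortable | number only, reading high as comfortable | 4–5 | Yes |

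The third row needs no mistake by the respondent. A family can find the revised plan simple to follow and still be uneasy about it; section 4 asks them to hold off treatment when sensor glucose is stable between 3.7 and 3.9 mmol/L on closed loop. Such a family ticks *Easy* correctly, and its discomfort goes unrecorded in item 3. The fifth row does need a misreading of the labels.

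**Step 3: what else on the form could pick this up.** Items 1, 4 and 6 go to every respondent. Item 1 invites reasons, but about the general recommendation. Item 4 concerns perceived time below 3 mmol/L. Item 6 is free comment. Any of them may bring discomfort to light; none asks for the reason behind the item 3 score.

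**Step 4: size.** A number would need the share of families whose ease and comfort differ and the share who answer by number and not by label. The protocol gives neither, and assumed values would only return the assumptions. The planned enrolment is 40 participants.

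**Step 5: reach.** The questionnaire is given once, after both periods, and item 3 concerns the revised threshold only. It yields no contrast between treatments, so the result can only be descriptive. The primary analysis and the sensor-derived outcomes do not use it.

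**The case against.** The strongest reply is that the labels settle the matter. All five boxes carry words, the instruction states both ends, and the follow-up repeats the labels. An uncomfortable family would have to tick a box marked *Very easy* or *Easy* to be misread, and most people would take the item as asking how easy or hard they found it. The stated outcome is open-ended questions, and the fear of hypoglycaemia survey, collected at Visits 1, 2 and 4, gives a separate rated check on worry.

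Much of this stands. Reversed ticking is unlikely, and the rest of the form gives families room to speak. It does not answer the mismatch of constructs: clear labels for ease do not help a family whose ease and comfort differ. The fear survey measures fear, not acceptability of this threshold.

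A reader might go further and infer that uncomfortable families with low scores are counted as accepting, are never asked why, and so bias the result towards the revised threshold. The document does not support this:

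- No rule treats a score of 1 or 2 as acceptance.
- Items 1, 4 and 6 are open to everyone, so the gap lies within item 3, not across the whole form.
- A one-way bias is not established. A comfortable family that wrongly ticks 5 and leaves the follow-up blank counts against the revised threshold. A family that found treatment hard but was comfortable looks worse on the score than its comfort warrants.

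**Conclusion.** The point holds as a wording defect in one questionnaire item. Stem and anchors do not match, so the score is a clean measure of neither comfort nor ease, and respondents scoring 1 or 2 are not asked about their score within the item. Both facts can be read directly from the form. PDF conversion could have changed the order of the stem and the boxes, but not their words.

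That the mismatch matters rests on one assumption: that ease and comfort can differ for some families. This is plausible here but is not quantified in the protocol, so no size can be given. The consequence is limited to a descriptive secondary outcome. This is a minor but worthwhile correction.

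**What to change.** Make the stem and the anchors of item 3 match, in one of two ways:

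- keep the present anchors and ask: *How easy or hard was it to treat hypos at this glucose level?*; or
- keep the comfort stem and replace the anchors with comfort anchors, with every box labelled in words.

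The first is the smaller edit and also removes the conflict over the direction of the numbers. With either, replace the follow-up limited to scores 3 to 5 by an invitation to every respondent to say why they chose their score.

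The cost is a one-line change to the form and a little more free text to read, with no added visits, participants or measurements. The downside is that forms already completed with the present wording cannot be pooled with the new ones on this item and must be reported separately.
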